### *Data Archiving*

Consent forms containing identifiable personal data will need to be retained for a minimum of 10 years, though will be archived separately to the study data collected. Data collated centrally will be archived by the East London NHS Foundation Trust, which is the host NHS trust sponsoring the study; participating sites will be responsible for archiving the study data that they hold based on their local policy.

## **6 STUDY SETTING**

This study will be coordinated by East London NHS Foundation Trust. Recruitment and data collection will take place in additional NHS England Trusts and care homes identified from Care Quality Commission websites and local authority and national registers, who have the capability and capacity to take part. aDIALOG+ sessions will take place face-to-face, and sessions with the research team will take place either face-to-face or remotely.

## **7 SAMPLE AND RECRUITMENT**

### **7.1 Eligibility Criteria**

#### **7.1.1 Inclusion and Exclusion Criteria**

##### WP1a

##### *Service Users Inclusion Criteria*

- Aged 18 or over
- Mild or moderate ID based on service records / clinical notes
- Current history of behaviour that challenges (at least one incident of self-injurious behaviour, physical aggression or damage to property in the last 3 months)
- Living in any setting including the family home and supported living/ residential home
- Can provide informed verbal or written consent

##### *Service Users Exclusion Criteria*

- Under 18 years of age
- Severe ID based on service records / clinical notes
- Likely to move out of borough within the next three months or at imminent risk of hospital admission
- Unable to provide informed verbal or written consent

##### *Clinicians Inclusion Criteria*

- Aged 18 or over
- Currently working within a community ID service, intensive support team or in a local authority or social care organisation for people with ID
- From any profession (e.g. psychology, nursing, speech and language therapy, psychiatry, social work), grade 4 and above with a minimum of six months experience working with people with ID
- Consent to participation

##### *Clinicians Exclusion Criteria*

- Under 18 years of age
- Not currently working within a community ID service, intensive support team or in a local authority or social care organisation for people with ID
- Below grade 4 and less than six months experience working with people with ID
- Do not consent to participation

### *Care Workers Inclusion Criteria*

- Aged 18 or over
- Have worked in the care home for at least three months
- Provide at least one day of support per week to service users
- Consent to participation

### *Care Workers Exclusion Criteria*

- Under 18 years of age
- Have worked in the care home for less than three months
- Do not provide at least one day of support per week to service users
- Do not consent to participation

## WP1b

### *Service Users Inclusion Criteria*

- Aged 18 or over
- Mild or moderate ID based on service records / clinical notes
- Under community ID services from the East London Foundation Trust
- Can provide informed verbal or written consent

### *Service Users Exclusion Criteria*

- Under 18 years of age
- Severe ID based on service records / clinical notes
- Not under community ID services from the East London Foundation Trust
- Unable to provide informed verbal or written consent

## WP2

### *Service Users Inclusion Criteria*

- Aged 18 or over
- Mild or moderate ID based on service records / clinical notes
- Current history of behaviour that challenges (at least one incident of self-injurious behaviour, physical aggression or damage to property in the last 3 months)
- Living in any setting including the family home and supported living/ residential home
- Can provide informed verbal or written consent

### *Service Users Exclusion Criteria*

- Under 18 years of age
- Severe ID based on service records / clinical notes
- Already participating in WP3 involved in another clinical trial
- Likely to move out of borough within the next six months or at imminent risk of hospital admission
- Unable to provide informed verbal or written consent

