## 2. Work package 1b: testing the psychometric properties of the aDIALOG quality of life scale

Research assistants will arrange a face-to-face meeting or conduct the assessment remotely on Teams or Zoom. We will collect basic socio-demographic data (gender, age, ethnicity, severity of ID, neurodevelopmental conditions, day activities, living arrangements, co-morbid psychiatric and physical illnesses) and we will ask service users to complete the aDIALOG scale and the following measures (in order to assess construct and concurrent validity):

- i. Mini-MANS LD and the WHOQOL Disabilities module (measures of quality of life in people with ID) (40, 41).
- ii. Clinical Outcome in Routine Evaluation- Learning Disability (CORE-LD), 14 item version (measure of psychological distress) (42).

In order to assess test re-test reliability, we will ask service users to complete the aDIALOG scale again on another occasion (ideally 24 hours later but no later than 1 week). This will be carried out face-to-face, online or via telephone.

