### *Clinicians Inclusion Criteria*

- Aged 18 or over

- Currently working within a community ID service, intensive support team or in a local authority or social care organisation for people with ID
- From any profession (e.g. psychology, nursing, speech and language therapy, psychiatry, social work), grade 4 and above with a minimum of six months experience working with people with ID
- Consent to participation
- Have not participated in other work packages

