### *Clinicians Exclusion Criteria*

- Under 18 years of age
- Not currently working within a community ID service, intensive support team or in a local authority or social care organisation for people with ID
- Below grade 4 and less than six months experience working with people with ID
- Do not consent to participation
- Have participated in other work packages

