### *Service Users Exclusion Criteria*

- Under 18 years of age
- Severe ID based on service records / clinical notes
- Already participating in WP2 or involved in another clinical trial
- Likely to move out of the care home within the next six months or are at imminent risk of hospital admission
- Unable to provide informed verbal or written consent

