### *Care Homes Inclusion Criteria*

- Supported living or residential placements for service users with ID in the participating areas
- Service manager has agreed for the care home to take part

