### *Care Homes Exclusion Criteria*

- Not supported living or residential placements for service users with ID and/or in the participating areas
- Service manager does not agree for the care home to take part

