## **7.2 Sampling**

### **7.2.1 Size of Sample**

- Work package 1a: 5 clinicians, 5 care workers and 20 service users.
- Work package 1b: 120 service users.
- Work package 2: 8-12 clinicians, 30 service users, and 10 participant carers.
- Work package 3: 10 care homes and their care workers (3-5 care workers in each care home, approx. 40 care workers). 3-5 service users in each care home (approximately 40 service users).

Total number of participants: clinicians - 17; care workers- 45; service users- 210; participant carers- 10.

For the feasibility study there is no formal sample size calculation but the sample size would need to be sufficient in order to estimate our main parameters of interest (recruitment and retention rates) and the precision of these estimates, allowing for the clustered nature of the data (Assuming an ICC of 0.04). If we anticipate a recruitment and retention rate of 75%, 12 clinicians, and 30 service users, would allow us to estimate 95% Confidence Intervals for recruitment and retention rates with a half width of 18%.

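### The WP2 and WP3 service-user criteria do not bar people who already received aDIALOG+ in WP1a, although staff must be new to every work package

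*Protocol*

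**What the plan says.** Section 7.1.1 of the Protocol lists eligibility by work package.

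- **WP2 service users** are excluded if "Already participating in WP3 involved in another clinical trial".
- **WP3 service users** are excluded if "Already participating in WP2 or involved in another clinical trial".
- **WP2 clinicians** must meet "Have not participated in other work packages", and the matching exclusion is "Have participated in other work packages". WP3 care workers carry the same pair of rules, and the section 5 design text repeats the requirement for both groups.

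Neither service-user list mentions WP1a or WP1b. The Study Summary and the section 5 design text for WP2 and WP3 do not mention them for service users either.

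In WP1a, five clinicians and five care workers each give aDIALOG+ at least once to two service users. In WP1b, 120 service users of the East London Foundation Trust (ELFT) complete the aDIALOG scale twice. They also complete the "Mini-MANS LD and the WHOQOL Disabilities module (measures of quality of life in people with ID") and the 14-item CORE-LD.

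**The concern.** Recruitment and retention are the principal objectives of WP2 and WP3. Someone who has already agreed to one part of the programme and completed it is not a typical new invitee. Such a person is plausibly more likely to agree again and to stay.

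A WP1a participant has also had at least one aDIALOG+ session, so the WP2 or WP3 baseline would follow exposure to the intervention. That baseline feeds three things:

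- the exploratory pre-post changes;
- the work on the minimal clinically important difference for ABC-Irritability, which uses change before and after aDIALOG+;
- the acceptability interviews, which would mix first-time and repeat users without a way to tell them apart.

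The protocol guards against prior participation among those who deliver the intervention. It does not do so among those who receive it and supply these data.

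**Working it through.** **1. Is overlap permitted?**

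| Element | WP1a | WP2 | WP3 |
|---|---|---|---|
| Age, mild or moderate ID, incident within 3 months, consent | required | required | required |
| Residence | any setting | any setting | supported living or residential care |
| Service-user bar on earlier participation | – | WP3 or another trial | WP2 or another trial |
| Service-user recruitment (Appendix schedules) | July 2025 | Oct 2025 to Feb 2026 | Oct 2025 to Feb 2026 |

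The WP1a and WP2 inclusion criteria are identical. The bar on another clinical trial does not clearly reach WP1a, which is a pilot within the same study. Section 5 asks WP2 and WP3 staff to approach all potentially eligible people until the target is met. So the criteria permit re-entry, and the approach rule does not filter it out.

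**2. How could it happen?** WP1a staff cannot serve in WP2 or WP3, so re-entry needs a different member of staff. Three routes remain:

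- a WP1a clinician's service user who is also on a new clinician's caseload;
- a WP1a care-home resident who is on a WP2 clinician's caseload;
- a WP1a participant living in a home later recruited to WP3.

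The ceiling is 5 × 2 + 5 × 2 = 20 people. The protocol gives nothing from which the actual number could be worked out.

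**3. The protocol's own precision figure, as a yardstick.** Section 7.2.1 assumes a rate of 75%, 12 clinicians, 30 service users and an ICC of 0.04.

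- Design effect = 1 + (30/12 − 1) × 0.04 = 1.06.
- Standard error = √(0.75 × 0.25 × 1.06 / 30) = 0.0814.
- Half-width with a t value on 11 degrees of freedom = 2.201 × 0.0814 = 17.9%, which reproduces the stated 18%. With z it is 1.96 × 0.0814 = 16.0%.

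**4. Bound on the shift.** Let k be the number of WP1a people among the 30 in WP2, and take 75% as the rate in new people. Retention in the k people cannot exceed 100%, so the expected upward shift is at most k × (1 − 0.75)/30.

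- k = 1: 0.8 points.
- k = 5: 4.2 points.
- k = 10: 8.3 points.
- k = 20, the ceiling: 16.7 points.

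For recruitment, 30 enrolled at 75% means 30/0.75 = 40 approached. The bound is then k × 0.25/40, or 0.6 points for k = 1 and 3.1 points for k = 5. The values of k are assumptions. The confidence interval would not reflect such a shift, because it is bias and not sampling error.

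**5. WP1b.** These people complete the aDIALOG scale, WHOQOL-DIS and CORE-LD 14. The last two return as WP2 and WP3 outcomes. WP1b runs from June to November 2025 and overlaps the first two baseline months, October and November. No sessions or action plans are given in WP1b.

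WP1b has no behaviour-that-challenges criterion, so only those with a recent incident could enter WP2 or WP3. If the 18% community figure in section 1 applied (an assumption; the rate among service users may be higher), that would be 0.18 × 120 ≈ 22 people, before any caseload or care-home restriction.

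**The case against.** The strongest reply is that existing rules already make overlap uncommon. WP1a staff are barred, WP3 recruits across East London, Bedfordshire and Cornwall, and section 7.3.1 draws WP2 clinicians from five NHS Trusts (although sections 7.2.2 and 7.3.2 say ELFT). This stands as a limit on size. It does not close the gap, because staff novelty does not make service users new.

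The different rule for staff is also defensible in itself, since earlier training and practice bear directly on fidelity. That explains why staff are barred. It does not explain why intervention recipients may re-enter unrecorded. The baseline form asks about psycho-social interventions received, which might catch WP1a exposure, but it does not name aDIALOG+ and no such use is planned.

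Direction is not certain either. Repeat participants could decline or drop out because of burden. Pre-post change is only exploratory in an uncontrolled study, and ABC-Irritability is not collected in WP1. These points stand and limit the consequence.

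A reader might infer more from three places, and the document does not support it:

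- **Head count.** The line "Total number of participants: clinicians - 17; care workers- 45; service users- 210; participant carers- 10" includes 20 + 120 + 30 + 40 = 210 service users. It is a sum of work-package targets and contradicts nothing.
- **Care homes.** The criteria ("Supported living or residential placements for service users with ID in the participating areas", and exclusion where "Service manager does not agree for the care home to take part") are silent on WP1a. The WP1a care workers are themselves barred, and barring a whole home would remove residents who were never exposed.
- **The missing conjunction** in the WP2 line. The WP3 line shows what was meant, so this is editorial.

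**Conclusion.** The gap is real and confined to the service-user criteria. As written, a person who received aDIALOG+ in WP1a can be enrolled in WP2 or WP3, counted in recruitment and retention, and assessed at a baseline that is not intervention-naive.

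It would be wrong to conclude that results will carry over from WP1, or that 140 exposed people stand in the pool. Overlap is allowed, not shown to be planned or likely. At most 20 people have had the intervention, and the WP1b group has had questionnaires only.

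On the protocol's 75% rate, each re-entered person can raise expected WP2 retention by at most 0.8 points. A handful would stay well inside the 18-point half-width. The upward direction is a judgement, and the number of people is unknown. This is an inexpensive improvement that protects the principal feasibility rates. It does not invalidate the design.

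**What to change.** Add *received aDIALOG+ in WP1a* to the WP2 and WP3 service-user exclusion criteria in section 7.1.1, and carry it into the matching design text in section 5.

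Do not exclude WP1b participants. Record WP1b participation as a yes/no field at baseline, and report recruitment, retention and change in scores with and without these people. For the recruitment rate, the same mark is needed on the screening record, so that those who decline are classified too.

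No care-home exclusion is needed. The missing conjunction in the WP2 line can be restored in the same edit.

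The cost is at most 20 potential participants, one baseline field and its counterpart at screening. Excluding WP1b participants as well could remove up to 120 more ELFT service users from the pool, which is why recording is preferable.

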### *Clinicians Inclusion Criteria*

- Aged 18 or over

- Currently working within a community ID service, intensive support team or in a local authority or social care organisation for people with ID
- From any profession (e.g. psychology, nursing, speech and language therapy, psychiatry, social work), grade 4 and above with a minimum of six months experience working with people with ID
- Consent to participation
- Have not participated in other work packages

### *Clinicians Exclusion Criteria*

- Under 18 years of age
- Not currently working within a community ID service, intensive support team or in a local authority or social care organisation for people with ID
- Below grade 4 and less than six months experience working with people with ID
- Do not consent to participation
- Have participated in other work packages

### *Participant Carers Inclusion Criteria*

- Aged 18 or over
- Are paid or unpaid (e.g. family carer); if a paid carer, need to have worked with the person for at least six months and should know the person well and support the person on a regular basis
- Consent to participation

### *Participant Carers Exclusion Criteria*

- Under 18 years of age
- If a paid carer and have worked with the person for less than six months and/or do not know the person well and/or support the person on a regular basis
- Do not consent to participation

## WP3

### *Service Users Inclusion Criteria*

- Aged 18 or over
- Mild or moderate ID based on service records / clinical notes
- Current history of behaviour that challenges (at least one incident of self-injurious behaviour, physical aggression or damage to property in the last 3 months)
- Residing in supported living or residential care
- Can provide informed verbal or written consent

### *Service Users Exclusion Criteria*

- Under 18 years of age
- Severe ID based on service records / clinical notes
- Already participating in WP2 or involved in another clinical trial
- Likely to move out of the care home within the next six months or are at imminent risk of hospital admission
- Unable to provide informed verbal or written consent

### *Care Homes Inclusion Criteria*

- Supported living or residential placements for service users with ID in the participating areas
- Service manager has agreed for the care home to take part

### *Care Homes Exclusion Criteria*

- Not supported living or residential placements for service users with ID and/or in the participating areas
- Service manager does not agree for the care home to take part

### *Care Workers Inclusion Criteria*

- Aged 18 or over
- Have worked in the care home for at least three months
- Provide at least one day of support per week to service users
- Consent to participation
- Have not participated in other work packages

### *Care Workers Exclusion Criteria*

- Under 18 years of age
- Have worked in the care home for less than three months
- Do not provide at least one day of support per week to service users
- Do not consent to participation
- Have participated in other work packages

## **7.2 Sampling**

### **7.2.1 Size of Sample**

- Work package 1a: 5 clinicians, 5 care workers and 20 service users.
- Work package 1b: 120 service users.
- Work package 2: 8-12 clinicians, 30 service users, and 10 participant carers.
- Work package 3: 10 care homes and their care workers (3-5 care workers in each care home, approx. 40 care workers). 3-5 service users in each care home (approximately 40 service users).

Total number of participants: clinicians - 17; care workers- 45; service users- 210; participant carers- 10.

For the feasibility study there is no formal sample size calculation but the sample size would need to be sufficient in order to estimate our main parameters of interest (recruitment and retention rates) and the precision of these estimates, allowing for the clustered nature of the data (Assuming an ICC of 0.04). If we anticipate a recruitment and retention rate of 75%, 12 clinicians, and 30 service users, would allow us to estimate 95% Confidence Intervals for recruitment and retention rates with a half width of 18%.

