##### 5. Acceptability:

Semi-structured interviews will be held with 6-10 clinicians, 10 service users and 10 participant carers supporting service users. We will use purposive sampling to identify service users who received at least half the sessions (3 or more), and those who received less than half the sessions (0-2 sessions) and we will interview clinicians from different backgrounds, and paid and family participant carers, in order to obtain a range of perspectives. Clinicians will be asked about their perspectives on the quality of training and supervision received, views about the ease of using the app and technical challenges and practical and organisational issues (e.g. time, resources) in implementing aDIALOG+. Topic guides for the service users will be developed with input from the PPI advisory group. The questions will include views about the accessibility and ease of using the app, perceived

benefits and unintended consequences of aDIALOG+, and aspects that did or did not work well and suggestions for improvements/changes. The interviews will be held after the collection of outcome data and will be conducted by a research assistant not involved in the collection of outcome data. The interviews will be audiotaped and transcribed verbatim using an approved transcription company. We will also ask clinicians to complete the NoMAD questionnaire (39) for assessing implementation processes from the perspective of professionals directly involved in the work of implementing complex interventions in healthcare.

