### Outcomes in service users

#### i. Behaviour that challenges

Changes in behaviour will be measured using the Aberrant Behaviour Checklist (ABC)-Irritability subscale (43). This is one of the five domains of the Aberrant Behaviour Checklist-Community (ABC-Community) and comprises 15 items rated on a 4-point Likert scale (0=never a problem; 3=severe problem). This will be completed by participant carers.

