#### vi. Global improvement

We will assess whether there are changes in behaviour and functioning as a result of the intervention (at 6 months) using a modified version of the Clinical Global Impressions Scale

(CGI) (46). The CGI global improvement measure (CGI-I) will be rated by the clinician (or care worker) delivering aDIALOG+, the service user and also the participant carer. The scale is rated from 1 (very much improved) to 7 (very much worse).

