### i. Health Related Quality of Life for service users

Changes in health-related quality of life in participants with ID will be assessed using the EuroQol Five Dimensions - Learning Disability version, a recently developed, modified version of the EQ-5D-3L (48, 49), which will be completed with service users. A proxy version of the EQ-5D-5L (50) will also be completed by participant carers.

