### iii. Service use

Information about health and social care contacts and medication in the preceding six months will be collected using a modified version of the Client Services Receipt Inventory (CSRI) (51). The CSRI has been used in previous economic evaluations in people with ID and will be adapted for use in this study (52). The number and duration of contacts with primary care, professionals within community ID services (e.g. psychiatrists, nurses, social workers), secondary care (outpatient, Accident and Emergency visits and hospital admissions), day services, medication, paid and unpaid carer input and contacts with criminal justice system, will be collected. All measures will be administered with participant carers but we will also explore the feasibility of collecting information using electronic patient records.

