Statistical analysis (work package 1b): We will examine the distribution, variability and mean/median scores for each of the items. In order to assess concurrent and convergent validity, we will examine spearman's correlation between the items relating to subjective quality of life on the aDIALOG scale and the other measures. We will assess test re-test reliability by calculating the intra class correlation coefficient (ICC). Items that show poor distribution, variability and poor test re-test reliability may be removed from the scale. We will measure the internal consistency of the items relating to subjective quality of life and the treatment aspects separately using Cronbach's alpha.

Statistical analysis (WP 2 and WP 3): The feasibility outcomes will be the main focus of analysis and descriptive statistics, with associated measures of precision appropriately accounting for clustering, will be used to assess recruitment and retention, adherence, response rates in completing the outcome measures, demographic and clinical data, and cost data. We will explore changes in the scores of the outcome measures using paired t-tests or non-parametric tests where appropriate. The primary outcome measure of changes in behaviour will be measured using the Aberrant Behaviour Checklist (ABC)- irritability subscale (43). For secondary outcomes we will measure changes in behaviour (Behaviour Problems Inventory- short form) (53), quality of life (WHOQOL Disabilities module) (40), community participation (Guernsey Community Participation and Leisure Assessment – Revised) (44), psychological distress (Clinical Outcomes in Routine Evaluation, 14 item version) (42), psychiatric disorders (Moss Psychiatric Assessment Schedule - Check) (45), global improvement (Clinical Global Impression Scale) (46), health related quality of life (modified version of the EQ-5D-3L for people with ID) (48, 49) and service use (the Client Services Receipt Inventory) (51). The frequencies of adverse and serious adverse events will also be reported.

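### The WP2 sample lists 10 participant carers for 30 service users, which does not fit a plan in which carers complete the primary outcome and four other service-user measures

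*Protocol*

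**What the plan says.** The Study Summary and section 7.2.1 give the same WP2 sample: "Work package 2: 8-12 clinicians, 30 service users, and 10 participant carers". Section 7.2.1 then adds up the programme: "Total number of participants: clinicians - 17; care workers- 45; service users- 210; participant carers- 10".

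The analysis text in section 5 (Data Storage and Analysis) names the primary outcome: "The primary outcome measure of changes in behaviour will be measured using the Aberrant Behaviour Checklist (ABC)- irritability subscale". The WP2 data-collection text says of that subscale: "This will be completed by participant carers". The same respondent is named for the community participation scale (GCPLA-R) and the Moss-PAS Check. For health-related quality of life, "A proxy version of the EQ-5D-5L (50) will also be completed by participant carers". For service use, "All measures will be administered with participant carers", although the same sentence goes on to say that electronic patient records will be explored as a source. Carers also report their own distress (K6) and their own EQ-5D-5L. The global improvement rating (CGI-I) "will be rated by the clinician (or care worker) delivering aDIALOG+, the service user and also the participant carer".

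The number 10 also appears under Acceptability: "Semi-structured interviews will be held with 6-10 clinicians, 10 service users and 10 participant carers supporting service users".

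The operational WP2 text has no such limit. Study Design has service users approached together with their carers. Data Collection has the researcher contact both and assess outcomes in both. Table 3 schedules carer screening, consent, baseline and 6-month questionnaires without restricting them to a subset.

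**The concern.** The sample-size list and the data-collection plan imply different numbers of carers. WP2 names no other informant for ABC-I; the rule that the main key worker completes informant measures belongs to WP3. Nor does the protocol say how many service users one carer may report on, or that informant measures are confined to a subset.

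Two stated aims depend on the answer. The proportion of participants completing each outcome is itself a WP2 feasibility outcome. If only 10 carers were enrolled, a low completion rate for the informant measures would reflect the enrolment number and say little about whether carers can and will complete them. The secondary objective of establishing a minimal clinically important difference (MCID) for ABC-I needs ABC-I change scores, whoever supplies the global rating to which they are linked.

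**Working it through.** **The plan's own figures.** The totals in 7.2.1 add up from the work packages:
- clinicians 5 + 12 = 17
- care workers 5 + 40 = 45
- service users 20 + 120 + 30 + 40 = 210
- participant carers 10, all from WP2

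So 10 enters the programme total as the whole planned carer sample.

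The stated half width of 18% also reproduces. With rate p = 0.75, 30 service users, 12 clinicians and ICC 0.04, the design effect is 1 + (30/12 − 1) × 0.04 = 1.06. The half width is t(0.975, 11 df) × √(0.75 × 0.25 × 1.06 / 30) = 2.201 × 0.0814 = 17.9%. Carers do not enter this calculation, so it is unaffected.

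**Who completes what in WP2.** Section 5 describes 11 outcome and economic instruments, leaving treatment costs aside:
- Participant carer, about the service user (5): ABC-I, GCPLA-R, Moss-PAS Check, proxy EQ-5D-5L, and the service-use inventory (CSRI, possibly supplemented by electronic records).
- Participant carer, about themselves (2): K6 and EQ-5D-5L.
- Three raters, one of them the carer (1): CGI-I.
- Service user only (3): WHOQOL-DIS, LD-CORE-14 and the learning-disability EQ-5D.

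**Coverage if 10 is the enrolment number.** Coverage = 10 × (service users per carer) / 30. Pairs at 6 months = covered service users × 0.75. The 75% is the protocol's anticipated recruitment and retention rate for WP2; applying it to carer-reported pairs is an assumption made here. The MCID pool is covered WP2 service users plus about 40 from WP3, before dropout.

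| Carer arrangement | Service users with ABC-I | Pairs at 75% | MCID pool |
|---|---|---|---|
| 10 carers, one service user each | 10/30 = 33% | 7.5 (7 to 8) | 10 + 40 = 50 |
| 10 carers, two each | 20/30 = 67% | 15 | 20 + 40 = 60 |
| 10 carers, three each on average | 30/30 = 100% | 22.5 (22 to 23) | 30 + 40 = 70 |
| 30 carers, one each | 30/30 = 100% | 22.5 (22 to 23) | 30 + 40 = 70 |

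In the first row, follow-up completion out of all 30 service users would be at most 7.5/30 = 25%.

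**Precision of the mean ABC-I change.** The 95% half width in SDs of change is t(0.975, n − 1)/√n, ignoring clustering:
- n = 7: 0.92; n = 8: 0.84
- n = 22: 0.44; n = 23: 0.43
- with no dropout, n = 10: 0.72; n = 30: 0.37

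With or without the 75% assumption, one-to-one coverage by 10 carers roughly doubles the half width.

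**The case against.** A reader might infer that two thirds of WP2 service users cannot have the primary outcome. The document does not support that, for two reasons. First, it assumes one carer per service user, which no section states. WP2 admits paid carers and people in supported or residential settings, so one paid carer could report on several people. Second, the operational text describes a carer alongside each service user and nowhere tells staff to stop at 10. On that reading the list understates the count, and there is no plan to leave people unassessed.

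Other limits also stand. K6 and the carer's own EQ-5D-5L are carer outcomes, so they are not data that service users would lack. The service-use inventory may draw on records. The MCID text links ABC-I change to ratings by service users, care workers or clinicians, so the anchor does not need the participant carer, and even the worst case keeps 50 of 70 service users. The 75% is not a coverage target for informant measures, so 67% coverage should not be judged a failure against it. Feasibility outcomes are the main focus of the analysis, and the precision calculation for recruitment and retention is sound.

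These points narrow the size of the problem without reconciling the text. Covering everyone with 10 carers needs an average of three service users each. That is planned nowhere, and it fits poorly with including family carers and with requiring a paid carer to have at least six months' work with the individual. If multiple reporting is intended, the protocol has to say so.

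**Conclusion.** The stated WP2 carer number is inconsistent with the protocol's own data collection, and the primary outcome is among the measures affected. How much is lost depends on how the number is applied. Enforced one-to-one, it limits ABC-I to 33% of service users and, assuming 75% retention, leaves 7 to 8 paired scores against 22 to 23 with full coverage. With two service users per carer the limit is 67%. If staff follow the operational text and enrol a carer for each service user, nothing is lost, but the sample size and programme total are then wrong.

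That the 10 was carried over from the interview subsample is an inference from the matching numbers; the document does not say so. A statistical analysis plan could not settle the matter, because it concerns who is enrolled and who supplies the data.

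**What to change.** In the Study Summary and section 7.2.1, restate WP2 as one participant carer per service user, up to 30, of whom 10 are interviewed. A smaller number is consistent only if the protocol also states that a paid carer may report on more than one service user. Correct the programme total for participant carers to match (30 in the one-to-one case). Report completion of informant measures out of all 30 service users, and record *no carer available* as a reason for non-completion. This is needed because the WP2 eligibility criteria do not require a service user to have a consenting carer.

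The cost is up to about 20 more carer consents, with two assessments each. Vouchers at GBP 20 for baseline and GBP 20 for follow-up come to 20 × 40 = GBP 800. Interview numbers and vouchers do not change, and no more service users or clinicians are needed. Researcher time for the extra assessments is a real cost that the document gives no figure for.
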